## 7.2 Analyses to support label update

This section outlines additional safety analyses needed to evaluate the impact of the implementation of the new pyrexia management guideline used in COMBI-A+ study.

The current dabrafenib and trametinib labels reflect the pyrexia management guidance in COMBI-d/v and COMBI-AD protocols; to interrupt dabrafenib if the patients temperature is  $\geq 38.5^{\circ}\text{C}$  and continue trametinib at the same dose. However, the increased incidence of pyrexia with combination compared to dabrafenib monotherapy, suggests that trametinib influences the dabrafenib -driven pyrexia process. Therefore, optimal guidance per current clinical consensus is to interrupt both dabrafenib + trametinib at the very first symptom of pyrexia or its associated prodrome (chills, rigors, night sweats or flu-like symptoms), as used in COMBI-i/COMBI-A+ protocols.

With a more proactive intervention for pyrexia, it is hypothesized that a cross-study comparison of pyrexia-related safety outcomes (e.g. incidence of grade  $\geq 3$  pyrexia, incidence of permanent discontinuations) in the metastatic melanoma setting (COMBI-d/v versus COMBI-i) and the adjuvant setting (COMBI-AD vs COMBI-A+) may support of a change to the dose modification section of the dabrafenib and trametinib labels. If warranted, the safety outputs defined in this SAP will be used to support the label update.

For the analyses related to complicated pyrexia and time spent in pyrexia, the following definitions will be used.

### Complicated pyrexia events

Subjects who have pyrexia (single preferred term (PT)) and any of the following terms at any time while on-treatment will be considered as having complicated pyrexia: severe ( $\geq$  Grade 3) chills, hypotension, dehydration, syncope, or renal dysfunction.

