 - prevent further episodes of pyrexia in those with recurrent pyrexia events i.e. prophylaxis
 - In subjects experiencing pyrexia higher than 40°C (104°F), and/or pyrexia associated with rigors, severe chills, dehydration or hypotension, serum creatinine and other evidence of renal function should be monitored frequently. The frequency of monitoring must be adapted based on the individual clinical presentation.
 - Clinical evaluation for infection and hypersensitivity is recommended for subjects experiencing pyrexia not resolving within 24 hours

Dabrafenib and trametinib can be interrupted in the presence of the pyrexia syndrome (i.e. chills or rigors or night sweats or flu-like symptoms without documented temperature $\geq 38^{\circ}\text{C}$ degrees) at investigators discretion for recurrent pyrexia and should be restarted upon improvement of symptoms at the same dose if symptom free for at least 24 hours.

If recurrent pyrexia cannot be managed with dabrafenib and trametinib interruption or prophylactic steroids, dose reduce as per [Table 6-5](#).

Pyrexia accompanied by hypotension, dehydration requiring intravenous fluids, renal insufficiency and/or severe (\geq Grade 3) rigors/chills in the absence of an obvious infectious cause should be reported as a SAE.

Guidelines for dose modification and management for pyrexia considered to be related to dabrafenib and/or trametinib are provided in [Table 6-4](#).

Table 6-4 Mandatory dose modification and recommended clinical management for pyrexia suspected to be related to dabrafenib and/or trametinib treatment

Pyrexia (≥ 38°C)		
Occurrence	Recommended adverse event management guidelines	Mandatory dose modification requirements

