## What is occurrence

If for a same patient, several consecutive AEs (**irrespective of study treatment causality, seriousness and severity**) occurred with the same SOC and PT:

- a single occurrence will be counted if there is  $\leq 1$  day gap between the end date of the preceding AE and the start date of the consecutive AE
- more than one occurrence will be counted if there is  $> 1$  day gap between the end date of the preceding AE and the start date of the consecutive AE

Specifically, the occurrence of AESI will follow the following rules.

To calculate the duration of AESI, the rule will be  $[\max(\text{end date of all below bullets}) - [\min(\text{start date of all below bullets})] + 1$ .

For the first occurrence of AESI, when subsequent records AE start date is same as first occurrence start date or end date is earlier than first occurrence end date

For the first occurrence of AESI, when subsequent records start date is after first occurrence start date, but is earlier than first occurrence end date

For the first occurrence of AESI, when subsequent records start date is after first occurrence start date, but is earlier than (previous latest occurrence end date + 7)

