## 4 Study design

This is an open-label Phase IIIb study of dabrafenib in combination with trametinib in the adjuvant treatment of melanoma after complete resection. Patients with completely resected, histologically confirmed, BRAF V600E/K mutation-positive, high-risk [AJCC ed. 8 Stage IIIA (lymph node metastasis >1 mm), IIIB, IIIC or IIID] cutaneous melanoma will be screened for eligibility. The main purpose of the study is to assess whether an adapted AE-management algorithm for pyrexia (Fever (> 38 °C)), will reduce the incidence of Grade 3/4 pyrexia, hospitalization due to pyrexia and permanent treatment discontinuation due to pyrexia. The effectiveness of dabrafenib and trametinib therapy in this setting will also be assessed based on RFS and OS.

As per the protocol amendment version dated 09-May-2019, approximately 600 subjects were planned to be enrolled to receive dabrafenib (150 mg BID) and trametinib (2 mg once daily) combination therapy for 12 months. Due to global drug supply availability, the enrollment of patients was slower than anticipated, resulting in the final sample of 556 enrolled patients in the study by the end of anticipated recruitment period. The final sample size is reasonably close to the planned target.

At enrollment, subjects will be instructed on the pyrexia management algorithm (refer to protocol Section 6.5.1.1). Doses of study treatment may be modified and/or interrupted for management of toxicities associated with study treatment.

Three analyses are planned for this study.

- The interim analysis (IA) based on primary endpoint and secondary endpoint conducted when 203 subjects were dosed for 6 months (either completed 6 months of treatment or discontinued earlier). The data cut-off date was 16 August, 2019.
- The primary analysis is planned to be performed at 12 months after the last patient first visit (LPFV). The data cut-off is planned on 26th September, 2020.

[figure not shown]
- The final analysis will be performed at the end of the study defined as 24 months after LPFV.

At the time of IA, an independent data monitoring committee (IDMC) recommended to continue the trial without any changes.

This study consists of two Periods for Enrolled subjects:

- Treatment Period – subjects will receive up to 12 months of treatment (refer to the schedule as noted in protocol Table 8-1).

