### **On-treatment assessment/event and observation periods**

For adverse event reporting the overall observation period will be divided into three mutually exclusive segments:

1. **pre-treatment period:** from day of patient's sign informed consent to the day before first administration of study treatment.
2. **on-treatment period:** from date of first administration of study treatment to 30 days after date of last actual administration of any study treatment: dabrafenib or trametinib (including start and stop date).
3. **post-treatment period:** starting at day 31 after last administration of study treatment.

For cases where time of assessment and time of treatment start/stop is captured (e.g. ECG's laboratory assessments), the last available assessment before the treatment period start/stop date/time will be used.

If dates are incomplete in a way that clear assignment to pre-, on-, and post-treatment period cannot be made, then the respective data will be assigned to the on-treatment period. Refer to [section 5.1.1](#) for imputation rules concerning AE start and stop dates.

Safety summaries (tables, figures) include only data from the on-treatment period with the exception of baseline data which will also be summarized where appropriate (e.g. change from baseline summaries). In addition, a separate summary for death including on treatment and post treatment deaths will be provided. In particular, summary tables for adverse events (AEs) will summarize only on-treatment events, with a start date during the on-treatment period (**treatment-emergent** AEs).

However, all safety data (including those from the post-treatment period) will be listed and those collected during the pre-treatment and post-treatment period will be flagged.

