**Table 2-6 Adverse events of special interest by study treatment**

	trametinib	dabrafenib	dabrafenib and trametinib combination
Hepatic disorders	x		x
Pneumonitis/Interstitial lung disease	x		x
Skin toxicities (e.g., rash, dermatitis acneiform)	x		x
Bleeding events	x		x
Hypersensitivity	x	x	x
Pancreatitis		x	x
Neutropenia			x
Pulmonary embolism, deep vein thrombosis	x		x
Pre-renal and intrinsic renal failure		x	x
New primary melanoma		x	x
Non-Cutaneous Treatment-Emergent Malignancies		x	x
Hyperglycemia		x	x
Cardiac related events	x		x
Complicated pyrexia and/or Grade 3 and Grade 4 pyrexia		x	x
Uveitis		x	x
Ocular events (e.g., retinal vein occlusion, retinal pigment epithelial detachment and uveitis)	x		x
Cutaneous squamous cell carcinoma including keratocanthoma		x	x
Hypertension	x		x

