### Percentage of time spent in pyrexia

Percentage of time spent in pyrexia AESI will be calculated for each subject who experienced a pyrexia AESI as follows:

$$\text{Total numbers of days in pyrexia AESI/ total duration of exposure in days} * 100.$$

The maximum duration of exposure to dabrafenib or trametinib will be used in the calculation.

The following tables will be required from this study. The tables generated outside protocol defined analyses, are flagged with (\*) in the below list.

- 1) Demographics and disease characteristics
- 2) Disease History
- 3) Summary of exposure and dose of study drug received for dabrafenib and trametinib
- 4) Dose interruptions of trametinib
- 5) Dose interruptions of dabrafenib
- 6) Summary of Concomitant Oral or IV Corticosteroids (\*)
- 7) Pyrexia AESIs leading to dose interruptions of trametinib (\*)
- 8) Pyrexia AESIs leading to dose interruptions of dabrafenib (\*)
- 9) Pyrexia AESIs leading to dose interruptions of both trametinib and dabrafenib (\*)
- 10) Pyrexia AESIs leading to dose reductions of trametinib (\*)
- 11) Pyrexia AESIs leading to dose reductions of dabrafenib (\*)
- 12) Pyrexia AESIs leading to dose reductions of both trametinib and dabrafenib (\*)
- 13) Summary of Pyrexia AESIs by maximum grade (\*)
- 14) Summary of Characteristics of Pyrexia AESIs (\*)
- 15) Time to onset and duration of first pyrexia AESI (\*)
- 16) AE leading to treatment discontinuation of trametinib
- 17) AE leading to treatment discontinuation of dabrafenib
- 18) AE leading to treatment discontinuation of both trametinib and dabrafenib
- 19) Pyrexia AESI leading to treatment discontinuation of trametinib (\*)
- 20) Pyrexia AESI leading to treatment discontinuation of dabrafenib (\*)
- 21) Pyrexia AESI leading to treatment discontinuation of both dabrafenib and trametinib (\*)
- 22) Summary of Pyrexia (Single Preferred Term) Complicated by Severe Chills, Hypotension, Dehydration, Syncope, or Renal Dysfunction (\*)
- 23) Summary of Skin-toxicity AESIs by Maximum Grade
- 24) Summary of Serious Pyrexia AESIs Requiring Hospitalization (\*)
- 25) Summary of Occurrences and percentage of time for Pyrexia AESIs (\*)
- 26) Event level Summary of Action Taken with Pyrexia AESI (\*)
- 27) Composite rate of grade 3/4 pyrexia, hospitalization or permanent treatment discontinuation due to pyrexia by 12 months

For all of the analyses mentioned in this SAP, pyrexia AESIs will be defined using the following list of PTs:

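### SAP 7.2 counts pyrexia as complicated without any time link between the fever and the complication, so the label-support table can only overstate a time-linked rate

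*SAP*

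**What the plan says.** SAP 7.2 introduces its rules for the label-update tables with "For the analyses related to complicated pyrexia and time spent in pyrexia, the following definitions will be used". Under the heading on complicated pyrexia events, subjects who have the single preferred term pyrexia and "any of the following terms at any time while on-treatment will be considered as having complicated pyrexia". The terms are chills of grade 3 or higher, hypotension, dehydration, syncope and renal dysfunction, the last limited to two preferred terms.

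SAP 5.1.1 sets the on-treatment period as running "from date of first administration of study treatment to 30 days after date of last actual administration of any study treatment", and SAP section 4 states that "subjects will receive up to 12 months of treatment". The two events may therefore lie up to about a year apart, in either order.

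The output is item 22 of the 27 tables listed in SAP 7.2: "Summary of Pyrexia (Single Preferred Term) Complicated by Severe Chills, Hypotension, Dehydration, Syncope, or Renal Dysfunction". SAP 7.2 places these tables in a cross-study comparison that may support a label change.

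In the protocol, section 6.5.1.1 states that "Pyrexia accompanied by hypotension, dehydration requiring intravenous fluids, renal insufficiency and/or severe" rigors or chills, without an obvious infectious cause, is to be reported as a serious adverse event. The same section describes a minority of fevers accompanied by such symptoms, and Table 6-4 speaks of fever complicated by dehydration or hypotension.

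**The concern.** The table title and the protocol describe a complication of a fever. The derivation counts something wider: two adverse events in the same subject at any time during treatment. Dehydration, hypotension and syncope have causes other than fever. Protocol 1.1.1.6 reports diarrhoea in 33% of the COMBI-AD combination arm, for example, which is another plausible route to dehydration. A subject with a simple fever and such an event months earlier or later enters the table as a complicated case.

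At stake is how a reader interprets a safety rate meant to show what the new pyrexia algorithm achieves. A rate that mixes true complicated fever with chance pairs overstates the first and can blur a difference between studies.

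**Working it through.** **Is there a time link anywhere else?** The only rules that join adverse-event records are in SAP section 2, under the heading on occurrence. They merge consecutive records that "occurred with the same SOC and PT", or records within one AESI. They join fever to fever and do not tie fever to a different term such as hypotension. No other section adds a window, an order or an attribution condition.

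**Direction.** Every subject who meets a time-linked rule also meets the any-time rule, so rate(any-time) ≥ rate(time-linked). The inequality is strict as soon as one subject has only an unlinked pair.

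**Size.** The plan gives no rate for complicated pyrexia, so there is no figure to reproduce. What follows is an illustration.

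Inputs from the documents:
- N = 556 (SAP section 4).
- p = 0.63, any pyrexia in the COMBI-AD combination arm (Protocol 1.1.1.6).
- Median exposure of 11 months in that arm (same section). With the SAP month of 30.4375 days and the 30-day tail, T = 11 × 30.4375 + 30 = 365 days.

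Assumptions, not in the documents:
- c = share of treated subjects with time-linked complicated pyrexia: 2% or 5%.
- q = share with an unrelated listed event on treatment: 1% to 10%.
- W = total days counted as linked to fever: 10 or 30.
- Unrelated events are independent of fever and uniform over time.

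Formula: any-time rate = c + (p − c) × q × (1 − W/T). The extra subjects are N times the second term.

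Example with c = 0.02, q = 0.05, W = 10: (0.63 − 0.02) × 0.05 × (1 − 10/365) = 0.0297. The any-time rate is 4.97%, and 556 × 0.0297 = 16.5 extra subjects.

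| c | q | W = 10: rate (extra subjects) | W = 30: rate (extra subjects) |
|---|---|---|---|
| 2% | 1% | 2.59% (3.3) | 2.56% (3.1) |
| 2% | 3% | 3.78% (9.9) | 3.68% (9.3) |
| 2% | 5% | 4.97% (16.5) | 4.80% (15.6) |
| 2% | 10% | 7.93% (33.0) | 7.60% (31.1) |
| 5% | 1% | 5.56% (3.1) | 5.53% (3.0) |
| 5% | 3% | 6.69% (9.4) | 6.60% (8.9) |
| 5% | 5% | 7.82% (15.7) | 7.66% (14.8) |
| 5% | 10% | 10.64% (31.4) | 10.32% (29.6) |

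The excess runs from about 3 to 33 subjects, or 0.5 to 5.9 points. The ratio to the time-linked rate is 1.3 to 4.0 when c = 2% and 1.1 to 2.1 when c = 5%.

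**The case against.** **The table is not produced at final analysis.** SAP section 2 leaves out the label-update analyses, and SAP section 3 lists this table (14.3.1-12.1) among those not needed. That stands, and it limits the point to the primary-analysis output. That output is still the one specified to support the label.

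**Complicated pyrexia is also an AESI.** A reader might infer that the row "Complicated pyrexia and/or Grade 3 and Grade 4 pyrexia" in the SAP's AESI table inherits the any-time rule. The documents do not support this. SAP 7.2 confines its definitions to its own analyses. SAP 5.8.1.2 takes AESI definitions from the Case Retrieval Strategy and defines pyrexia AESIs by nine preferred terms that include no complication.

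**The protocol does not define the term.** Section 6.5.1.1 gives a reporting instruction, its list differs (it has no syncope, and dehydration must need intravenous fluids), and the protocol's AESI table names complicated pyrexia without defining it. So the SAP does not breach a protocol definition. What remains is that the rule does not match the concurrent meaning used in that section and in the table's title.

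**The same rule in every study would cancel the error.** It might narrow the error, but the SAP does not say which rule the comparator studies used. Even with a common rule, a shared background dilutes a contrast. Suppose true rates of 5% and 2.5% (ratio 0.50) and q = 5%, ignoring W. The rates become 0.05 + 0.58 × 0.05 = 7.9% and 0.025 + 0.605 × 0.05 = 5.5%, a ratio of 0.70. A reader might infer that the rule favours the new algorithm. Nothing in the documents shows that, and dilution would work against it.

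**Other limits may undercount.** The single pyrexia term, the grade 3 threshold for chills and the two renal terms can miss cases. The net error against true complicated fever is therefore unknown. The point concerns only the missing time link.

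**Conclusion.** The point holds in a limited form. The stated rule labels unlinked pairs as complications of fever, and its rate can only equal or exceed a time-linked one. That direction needs no assumption.

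The size does. The range of 3 to 33 of 556 subjects rests on an assumed 1% to 10% with an unrelated listed event, on independence, and on COMBI-AD figures for fever and exposure. It would be tempting to say that the excess matches the 5% grade 3/4 pyrexia rate in COMBI-AD. That needs the top of the assumed range, for which the documents give no source.

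The primary composite endpoint does not use this definition and is unaffected. So are the final re-run and, as far as the documents show, the AESI summaries. The change is worth making because a table offered for labelling should measure what its title says.

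**What to change.** Make the main row of the primary-analysis table time-linked. Count a subject only if a listed event overlaps a pyrexia episode, or starts within a pre-stated short window before the episode begins or after it ends. The window before onset is needed because SAP 7.2 describes chills and rigors as a prodrome of fever, and a rule that required onset on or after the fever would lose true cases.

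Keep the any-time count as a supplementary row, labelled as co-occurrence. Apply both rows to the comparator studies. State how an episode is built, since SAP section 2 uses gaps of both 1 and 7 days. State also how incomplete dates are handled: the SAP's end-date imputation extends a fever with no end date to the end of the on-treatment period, which would link it to every later event.

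The cost is derivation code on adverse-event start and end dates that are already collected. The drawbacks are that comparator data must be re-derived and that the window length is a judgement, so showing two lengths would be sensible. If the table has already been issued, the time-linked row can be added and marked as specified afterwards.

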### Percentage of time spent in pyrexia

Percentage of time spent in pyrexia AESI will be calculated for each subject who experienced a pyrexia AESI as follows:

$$\text{Total numbers of days in pyrexia AESI/ total duration of exposure in days} * 100.$$

The maximum duration of exposure to dabrafenib or trametinib will be used in the calculation.

The following tables will be required from this study. The tables generated outside protocol defined analyses, are flagged with (\*) in the below list.

- 1) Demographics and disease characteristics
- 2) Disease History
- 3) Summary of exposure and dose of study drug received for dabrafenib and trametinib
- 4) Dose interruptions of trametinib
- 5) Dose interruptions of dabrafenib
- 6) Summary of Concomitant Oral or IV Corticosteroids (\*)
- 7) Pyrexia AESIs leading to dose interruptions of trametinib (\*)
- 8) Pyrexia AESIs leading to dose interruptions of dabrafenib (\*)
- 9) Pyrexia AESIs leading to dose interruptions of both trametinib and dabrafenib (\*)
- 10) Pyrexia AESIs leading to dose reductions of trametinib (\*)
- 11) Pyrexia AESIs leading to dose reductions of dabrafenib (\*)
- 12) Pyrexia AESIs leading to dose reductions of both trametinib and dabrafenib (\*)
- 13) Summary of Pyrexia AESIs by maximum grade (\*)
- 14) Summary of Characteristics of Pyrexia AESIs (\*)
- 15) Time to onset and duration of first pyrexia AESI (\*)
- 16) AE leading to treatment discontinuation of trametinib
- 17) AE leading to treatment discontinuation of dabrafenib
- 18) AE leading to treatment discontinuation of both trametinib and dabrafenib
- 19) Pyrexia AESI leading to treatment discontinuation of trametinib (\*)
- 20) Pyrexia AESI leading to treatment discontinuation of dabrafenib (\*)
- 21) Pyrexia AESI leading to treatment discontinuation of both dabrafenib and trametinib (\*)
- 22) Summary of Pyrexia (Single Preferred Term) Complicated by Severe Chills, Hypotension, Dehydration, Syncope, or Renal Dysfunction (\*)
- 23) Summary of Skin-toxicity AESIs by Maximum Grade
- 24) Summary of Serious Pyrexia AESIs Requiring Hospitalization (\*)
- 25) Summary of Occurrences and percentage of time for Pyrexia AESIs (\*)
- 26) Event level Summary of Action Taken with Pyrexia AESI (\*)
- 27) Composite rate of grade 3/4 pyrexia, hospitalization or permanent treatment discontinuation due to pyrexia by 12 months

For all of the analyses mentioned in this SAP, pyrexia AESIs will be defined using the following list of PTs:

Pyrexia PT	PT Code
Body temperature increased	10005911
Cytokine release syndrome	10052015
Hyperpyrexia	10020741
Hyperthermia	10020843
Influenza like illness	10022004
Pyrexia	10037660
Sweating fever	10042666
Systemic inflammatory response syndrome	10051379
Tumour associated fever	10052243

For complicated pyrexia analyses, renal dysfunction will be defined using the following list of PTs:

Renal Dysfunction PT	PT Code
Prerenal failure	10072370
Acute kidney injury*	10069339

\*PT Acute renal failure was replaced by Acute kidney injury in MedDRA 24.1 They are equivalent terms.

